3.5 Handling of Endpoints

3.5.1 Montgomery Åsberg Depression Rating Scale (MADRS)

The MADRS total score will be the sum of scores for MADRS Items 1 through 10.

3.5.2 Clinical Global Impression – Improvement (CGI-I)

“0. Not assessed” will be handled as missing data.

3.5.3 Clinical Global Impression - Severity of Illness (CGI-S)

“0. Not assessed” will be handled as missing data.

3.5.4 Hamilton Rating Scale for Depression (HAM-D)

The HAM-D 17-item total score will be the sum of scores for HAM-D Items 1 through 17.

3.5.5 Sheehan Disability Scale (SDS)

The mean SDS score will be the mean of scores for 3 SDS items (work/school, social life, and family life/home responsibilities). In the case of a missing score for work/school, the mean of scores for the other 2 items will be handled as the mean SDS score.

3.5.6 Drug-induced Extrapyramidal Symptoms Scale (DIEPSS)

The DIEPSS total score will be the sum of scores for DIEPSS items 1 through 8.

3.5.7 Abnormal Involuntary Movement Scale (AIMS)

The AIMS total score will be the sum of scores for AIMS items 1 through 7.

4 Sample Size

To verify the safety of long-term administration, the target number of subjects to complete 52 weeks of administration was set at around 100 subjects. Due to the availability of data on safety in elderly subjects from foreign clinical trials, the sample size needed to assess the safety of brexpiprazole in the elderly was set as 30 new subjects (elderly subjects of age 65 and above) receiving IMP administration.

5 Statistical Analysis Datasets

In this trial, unless otherwise specified, analysis will be performed for each of the following groups:

- Rollover subjects from the double-blind trial (331-102-00058) who were assigned to the brexpiprazole groups in the double-blind period (Phase B)
- Rollover subjects from the double-blind trial (331-102-00058) who were assigned to the placebo group in the double-blind period (Phase B)
- All rollover subjects from the double-blind trial (331-102-00058)
- New subjects (elderly subjects aged 65 years or older)
- All subjects (rollover and new subjects combined)

5.1 Efficacy Analysis Set

The efficacy analysis set will comprise subjects who have received at least 1 dose of the IMP, and from whom MADRS total scores have been obtained at baseline and at least 1 time point after initiation of the treatment. Subjects who did not comply with Good Clinical Practice (GCP) will be excluded.

5.2 Safety Analysis Set

The safety analysis set will comprise subjects who have received at least 1 dose of the IMP. Subjects who did not comply with GCP will be excluded.

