### **3.13 Protocol Deviations**

In the event of a significant deviation from the protocol due to an emergency, accident, or mistake (eg, violation of informed consent process, IMP dispensing or subject dosing error, treatment assignment error, subject enrolled in violation of eligibility criteria or concomitant therapy criteria), the investigator, subinvestigator, or designee will contact the sponsor at the earliest possible time by telephone. The investigator or subinvestigator and sponsor will come as quickly as possible to a joint decision regarding the subject's continuation in the trial. This decision will be documented by the investigator or subinvestigator and the sponsor, and reviewed by the site monitor. For major deviations, the date on which the deviation occurred and the details of the deviation will be recorded in the source documents and the CRF.

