#### **7.2.2 Safety Analysis Set**

The safety analysis set will comprise subjects who have received at least 1 dose of the IMP.

Unless otherwise specified, analysis will be performed for each of the following groups:

- Rollover subjects from the double-blind trial (331-102-00058) who were assigned to the brexpiprazole groups in the double-blind period (Phase B)
- Rollover subjects from the double-blind trial (331-102-00058) who were assigned to the placebo group in the double-blind period (Phase B)
- All rollover subjects from the double-blind trial (331-102-00058)
- New subjects (elderly subjects aged 65 years or older)
- All subjects (rollover and new subjects combined)

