7.6 Protocol Deviations

Numbers and proportions of subjects with major deviations from the protocol will be determined for each category (treatment-related deviations, eligibility-related deviations, a failure to discontinue the trial when the subject meets the withdrawal criteria, procedure-related deviations that affect evaluation of the primary endpoint, use of prohibited medications, and overall) and each trial site, in the safety analysis set.

8 Efficacy Analysis

Efficacy analysis will be performed using the efficacy analysis set. Baseline is defined as the last data obtained prior to initiation of IMP treatment in the trial.

- MADRS total score
- CGI-S
- CGI-I
- HAM-D 17 total score
- Mean SDS score and score for each item

Descriptive statistics of actual measurements and changes from baseline at each time point and the last assessment time point (Week 52 LOCF) will be determined.

- MADRS response rate (proportion of subjects in whom MADRS total scores have been reduced by at least 50% from baseline)
- MADRS remission rate (proportion of subjects in whom MADRS total scores have been reduced by at least 50% from baseline, with their resultant MADRS total scores being ≤ 10)
- CGI-I improvement rate (proportion of subjects who score 1 or 2 on the CGI-I scale)
Numbers and proportions of subjects will be determined at each time point and the last assessment time point (Week 52 LOCF).

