8.1 Subgroup Analyses

No subgroup efficacy analyses will be performed.

9 Other Analyses

Other analyses will be performed using the efficacy analysis set. Baseline is defined as the last data obtained prior to initiation of IMP treatment in the trial.

- EuroQol-5 Dimension, 5 response level version (EQ-5D-5L)
For each item, descriptive statistics of actual measurements and changes from baseline at each time point and the last assessment time point (Week 52 LOCF) will be determined.

10 Safety Analyses

Safety analysis will be performed using the safety analysis set. Baseline is defined as the last data obtained prior to initiation of IMP treatment in the trial.

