10.7.3 Columbia-Suicide Severity Rating Scale (C-SSRS)

Numbers and proportions of subjects for each C-SSRS item (suicidality, suicidal ideation, suicidal behavior, completed suicide, emergence of suicidal ideation, emergence of serious suicidal ideation, worsening of suicidal ideation, and emergence of suicidal behavior) at each time point and in the overall period after initiation of IMP treatment (including the post-treatment observation period, at discontinuation, and unscheduled visits) will be determined. A listing of subjects with emergence of suicidal ideation, emergence of serious suicidal ideation, worsening of suicidal ideation, and emergence of suicidal behavior will be provided. Items of suicidal ideation and suicidal behavior will also be summarized in the same manner.

- Suicidality: “Yes” for any item of suicidal ideation or suicidal behavior
- Suicidal ideation: “Yes” for any item of suicidal ideation
- Suicidal behavior: “Yes” for any item of suicidal behavior
- Emergence of suicidal ideation: Change from “No” at baseline to “Yes” after baseline for suicidal ideation
- Emergence of serious suicidal ideation: Change from “No” at baseline to “Yes” with Grade 4 or 5 after baseline for suicidal ideation
- Worsening of suicidal ideation: Increase in the grade of suicidal ideation from baseline
- Emergence of suicidal behavior: Change from “No” at baseline to “Yes” after baseline for suicidal behavior

11 Pharmacokinetic Analyses

Not applicable.

12 Pharmacodynamic Analyses

Not applicable.

13 Pharmacogenomic Analyses

Not applicable.

14 Interim Analysis

None.

15 Changes in the Planned Analyses

- The following changes were made to categorical analyses of QTc:
 - Only subjects with postdose QTc meeting the criteria will be summarized, instead of summarization at all time points.
 - Only subjects with QTc not meeting the criteria at baseline and meeting the criteria after baseline will be summarized.
- C-SSRS will be analyzed in the overall period after initiation of IMP treatment, not at the last assessment time point.

16 References

Not applicable.

17 History of Amendments

Table 17-1 History of Amendments		
Version	Date	Major Changes
1.0	01 Jun 2021	Not applicable

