2.0	19 Jul 2022	
 Exclusion of subjects who did not comply with GCP was added to the definition of analysis sets in Section 5 Statistical Analysis Datasets. The wording “Agranulocytosis, neutropenia, leukopenia” was replaced with the more appropriate term “Blood disorder-related AEs” in Section 10.2.1 Adverse Events of Interest. A typographical error in Section 15 Changes in the Planned Analysis was corrected (before correction: “after initiation of after IMP treatment”; after correction: “after initiation of IMP treatment” (Please note that this error had been made only in the Japanese version and no correction was necessary in the English version.)

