- CT-7.2 Extent of Exposure to ADT (Safety Analysis Set)
- CT-7.3 Summary of Treatment Compliance (Efficacy Analysis Set)
- CT-8.1 Adverse Events (All Causalities) (Safety Analysis Set)
- CT-8.2.1 Incidence of TEAEs by MedDRA System Organ Class and Preferred Term (Safety Analysis Set)
- CT-8.2.2 Incidence of Drug-related TEAEs by MedDRA System Organ Class and Preferred Term (Safety Analysis Set)
- CT-8.3.1 Incidence of TEAEs by MedDRA System Organ Class, Preferred Term and Severity (Safety Analysis Set)
- CT-8.3.2 Incidence of Drug-related TEAEs by MedDRA System Organ Class, Preferred Term and Severity (Safety Analysis Set)
- CT-8.4.1 Incidence of Deaths due to TEAEs by MedDRA System Organ Class and Preferred Term (Safety Analysis Set)
- CT-8.4.2 Incidence of Deaths due to Drug-related TEAEs by MedDRA System Organ Class and Preferred Term (Safety Analysis Set)
- CT-8.5.1 Incidence of Serious TEAEs by MedDRA System Organ Class and Preferred Term (Safety Analysis Set)
- CT-8.5.2 Incidence of Serious Drug-related TEAEs by MedDRA System Organ Class and Preferred Term (Safety Analysis Set)
- CT-8.6.1 Incidence of TEAEs Resulting in Discontinuation of IMP by MedDRA System Organ Class and Preferred Term (Safety Analysis Set)
- CT-8.6.2 Incidence of Drug-related TEAEs Resulting in Discontinuation From Study by MedDRA System Organ Class and Preferred Term (Safety Analysis Set)
- CT-8.7.1 Incidence of TEAEs of at Least 2% in Any Group by MedDRA System Organ Class and Preferred Term (Safety Analysis Set)
- CT-8.7.2 Incidence of Drug-related TEAEs of at Least 2% in Any Group by MedDRA System Organ Class and Preferred Term (Safety Analysis Set)
- CT-8.8.1 Incidence of TEAEs by MedDRA System Organ Class, Preferred Term and Time to First Onset (Safety Analysis Set)
- CT-8.8.2 Incidence of Drug-related TEAEs by MedDRA System Organ Class, Preferred Term and

	Time to First Onset (Safety Analysis Set)
CT-8.9.1	Incidence of TEAEs for EPS (Safety Analysis Set)
CT-8.9.2	Incidence of TEAEs for Neuroleptic Malignant Syndrome (Safety Analysis Set)
CT-8.9.3	Incidence of TEAEs for Rhabdomyolysis and CPK Elevation (Safety Analysis Set)
CT-8.9.4	Incidence of TEAEs for Seizures (Safety Analysis Set)
CT-8.9.5	Incidence of TEAEs for Orthostatic Hypotension, Dizziness, and Syncope (Safety Analysis Set)
CT-8.9.6	Incidence of TEAEs for Suicidality (Safety Analysis Set)
CT-8.9.7	Incidence of TEAEs for Somnolence (Safety Analysis Set)

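### The SAP removes treated subjects from the safety set for undefined GCP non-compliance, against the protocol's all-treated definition, and its section on changed analyses does not list this

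*SAP*

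**What the plan says.** Protocol 7.2.2 defines the set by exposure alone: "The safety analysis set will comprise subjects who have received at least 1 dose of the" IMP. It gives no exception.

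SAP 5.2 repeats that definition and adds: "Subjects who did not comply with GCP will be excluded". SAP 5.1 adds the same exclusion to the efficacy set, where protocol 7.2.1 has none.

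The SAP's amendment history (section 17) records the change under version 2.0, dated 19 Jul 2022: "Exclusion of subjects who did not comply with GCP was added to the definition of analysis sets". It gives neither a reason nor a criterion.

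SAP section 15, Changes in the Planned Analyses, has two entries. The first opens "The following changes were made to categorical analyses of QTc"; the second concerns the period over which the C-SSRS is summarised. Neither mentions an analysis set.

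SAP section 10 states: "Safety analysis will be performed using the safety analysis set".

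**The concern.** The SAP narrows a population that the protocol defines, and the rule that narrows it cannot be applied reproducibly. Neither document says what GCP non-compliance by a subject is, who decides that it occurred, or when. Elsewhere GCP is a standard for consent forms, site participation, site files, monitoring and trial conduct, not a duty of subjects. One programmer could remove only subjects with a consent failure; another could remove everyone at a site with a conduct breach. Both would be following the text.

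Safety is a main purpose of this trial. The completer target and the elderly group of 30 were both set to assess safety, and SAP section 6 plans no primary or secondary outcome. The descriptive safety tables are therefore a core product. If treated subjects can drop out of them under an undefined rule, the reported rates are not the all-treated rates that the protocol defines.

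**Working it through.** The documents give no figure to reproduce: the number of excluded subjects is not stated, and both sample-size targets were set without a formula. The check is a comparison of the texts, followed by an illustration of size.

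**1. Is there a definition elsewhere?**
- Protocol 3.13 gives "violation of informed consent process" as an example of a significant deviation. It provides for a joint decision on whether the subject continues and does not link deviations to analysis sets.
- SAP 7.6 names five deviation categories: treatment, eligibility, failure to withdraw a subject who met the withdrawal criteria, procedures affecting the primary endpoint, and prohibited medication. None is GCP or consent non-compliance.
- So neither section supplies the missing criterion.

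**2. What would lose the excluded subjects?**
- The section 10 summary tables in SAP Appendix 5 labelled Safety Analysis Set, including all TEAEs, serious TEAEs and deaths due to TEAEs.
- Reasons for discontinuation in CT-2.1, which uses the safety set.
- The major-deviation table itself. SAP 7.6 counts deviations by category, ending "use of prohibited medications, and overall) and each trial site, in the safety analysis set". A subject removed for misconduct would thus also leave the table of misconduct.

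**3. What would still show them?**
- SAP 7.1 counts subjects in each analysis set and discontinuations by reason; CT-1.1 is on enrolled subjects.
- AE-1, DREAS-1, PDATA-3, PDEV-1 and SUBEX-1 cover subjects assigned to treatment.
- CT-9.1 to CT-9.3 (deaths, serious events, discontinuations due to adverse events) carry no set label.

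**4. Size, under assumptions.** Inputs: 30 treated elderly subjects (protocol 7.1); one serious event (assumed); one or three exclusions (assumed). The exact two-sided 95% upper limit *p* solves P(X ≤ x | n, p) = 0.025. For x = 0 this is p = 1 − 0.025^(1/n), so for n = 29 it is 1 − 0.025^(1/29) = 11.9%. For x = 1 it solves (1 − p)^n + n·p·(1 − p)^(n−1) = 0.025.

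| Case | Rate | Upper limit |
|---|---|---|
| All treated | 1/30 = 3.3% | 17.2% |
| One removed, with the event | 0/29 = 0% | 11.9% |
| One removed, event-free | 1/29 = 3.4% | 17.8% |
| Three removed, including the event | 0/27 = 0% | 12.8% |
| Three removed, all event-free | 1/27 = 3.7% | 19.0% |

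In a group of 100 with two events (also assumed), removing one subject who had an event takes the rate from 2/100 = 2.0% to 1/99 = 1.0%.

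**5. Precision alone.** With zero events, the one-sided 95% upper limit is 1 − 0.05^(1/n). It goes from 9.5% (n = 30) to 10.5% (n = 27), and from 2.95% (n = 100) to 3.04% (n = 97). The loss of precision is small. What matters is whose events are removed.

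**The case against.** The strongest reply is that the change is open and its effect can be traced. Section 17 names it first among the version 2.0 changes, with date and section. SUBEX-1 lists the excluded subjects, AE-1 shows their events, and CT-9.1 and CT-9.2 list deaths and serious events without a set restriction. Discontinuation reasons survive in the disposition summary, DREAS-1 and PDATA-3. A careful reader could rebuild the all-treated counts.

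It can also be said that the rule may mean only subjects without valid consent, whose data may be unusable; that the phrase may be awkward translation, since a Japanese version exists; that protocol section 7 leaves detail to a SAP finalised before data lock, and no lock date is given, so no timing breach is shown; and that the illustration uses the smallest group and assumed events, with confidence limits that SAP 10.2 does not plan to report.

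Much of this stands. The change is recorded, the listings are real safeguards, and the size is hypothetical. Nothing shows that anyone was excluded or that outcomes prompted the rule. But listings do not correct a rate or its denominator, and a log entry without a criterion does not say who is excluded. If only consent failures were meant, the text does not say so.

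**Conclusion.** The concern holds on all three parts: SAP 5.2 conflicts with protocol 7.2.2, the exclusion has no criterion, and section 15 does not declare it. The last part is limited to section 15, because section 17 does record the change.

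The textual conflict is certain; its effect on results is unknown, because the number excluded is not given. Precision would hardly change. The exposure is to selective loss of events in small groups: under the assumptions above, one exclusion among 30 elderly subjects can turn a 3.3% serious-event rate into zero, or raise it slightly to 3.4%. Version 2.0 is dated 12 days before the trial's stated end of 31 Jul 2022, and the trial is open-label. That is no evidence of data-driven selection, but it is a reason to have the criterion in writing. The plan should be corrected on this point.

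**What to change.** - **SAP 5.2:** restore the protocol definition, all subjects with at least one dose, for the main safety tables. Confine any GCP-based exclusion to a supplementary safety run or to the efficacy set.
- **Narrow exception:** if some data cannot lawfully be used, for example because there is no valid consent, state that criterion in SAP 5.2, name who decides, and fix the decisions before data lock.
- **SAP section 15:** declare the change, including the parallel exclusion in SAP 5.1.
- **Main TEAE tables:** add a footnote with the number of treated subjects excluded and, where permitted, their serious events and deaths.

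The cost is wording in SAP 5.2 and section 15, one footnote, and at most one supplementary run of the main TEAE tables. No new data are needed, because SUBEX-1 already lists excluded subjects.

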5.3 Handling of Missing Data

The analysis of last assessment time point will be performed using the last observation carried forward method (herein after referred to as "LOCF"), by which missing data at Week 52 will be imputed by the last observed data after initiation of IMP treatment.

6 Primary and Secondary Outcome Variables

Neither primary nor secondary outcome variables are planned.

7 Disposition and Demographic Analysis

7.1 Subject Disposition

Numbers and proportions of subjects from whom informed consent was obtained, those who received trial treatment, those who completed the trial, those who discontinued the trial, those who discontinued the trial by reason, and those included in each analysis set will be summarized. Similar summarization will be performed for each requisite concomitant medication.

Numbers and proportions of subjects who completed the trial will be summarized for each period (days) (1-7, 8-14, 15-28, 29-56, 57-84, 85-112, 113-140, 141-168, 169-196, 197-224, 225-252, 253-280, 281-308, 309-336, 337-364, > 364).

7.2 Demographic and Baseline Characteristics

Descriptive statistics (mean, standard deviation, minimum, median, maximum; hereinafter the same applies) of age, height, body weight, waist circumference, and body mass index (BMI) and frequency distribution of sex, race, ethnicity, country where trial is conducted, medical history, and complications will be determined in each analysis set. Similar summarization will be performed for each requisite concomitant medication.

In rollover subjects, baseline data in the present trial will be used for body weight, waist circumference, and BMI. For medical history and complications, baseline data in the present trial as well as in the double-blind trial (331-102-00058) will be used. For the other demographic characteristics, baseline data in the double-blind trial (331-102-00058) will be used.

7.3 Baseline Disease Evaluation

Descriptive statistics of the duration (months) of the current major depressive episode, age at initial onset, duration (months) of major depressive episode from initial onset, MADRS total score, HAM-D17 total score, and CGI-S and frequency distribution of DSM-5-based diagnosis (single, recurrent), severity (mild, moderate, severe), specific terms (“not applicable,” “applicable,” and disposition of each specific term), frequency of major depressive episodes (1, 2, 3, 4, ≥ 5), frequency of appropriate antidepressant drug treatments of the current major depressive episode (1, 2, 3) will be determined in each analysis set. Similar summarization will be performed for each requisite concomitant medication.

In rollover subjects, baseline data in the present trial will be used for MADRS total score, HAM-D17 total score, and CGI-S. For the other demographic characteristics, baseline data in the double-blind trial (331-102-00058) will be used.

The duration of the current major depressive episode and the duration of major depressive episode from initial onset will be calculated using the following formula: duration (months) = (date of subject demographic evaluation – date of onset + 1) / 30. Any unknown month or day of onset will be replaced with June or 15, respectively.

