
Criteria for Evaluation
	
Safety Endpoints: Adverse events, clinical laboratory tests, vital signs (body temperature, diastolic blood pressure and systolic blood pressure and pulse rate [supine, sitting, and standing positions]), physical examination, waist circumference, 12-lead ECG, body weight, body mass index, C-SSRS, DIEPSS, AIMS, BARS
 
Efficacy Endpoints:
 
 
• Mean changes from baseline in MADRS total scores
 
• MADRS response rate The proportion of subjects in whom MADRS total scores have been reduced by at least 50% from baseline
 
• MADRS remission rate The proportion of subjects in whom MADRS total scores have been reduced by at least 50% from baseline, with their resultant MADRS total scores being <math>\leq 10</math>
 
• CGI-I improvement rate The proportion of subjects who score 1 or 2 on the CGI-I scale
 
• Mean changes from baseline in CGI-S
 
• Mean changes from baseline in HAM-D 17-item total score
 
• Mean changes from baseline in mean SDS score
 
 
Other Endpoints: EQ-5D-5L

Statistical Methods:
	
Safety analysis Incidences of treatment-emergent adverse events will be determined. Descriptive statistics of actual measurements at each assessment time point and the last assessment time point (Week 52 LOCF) as well as changes from baseline will be determined.
 
Efficacy analysis

Descriptive statistics of actual measurements at each assessment time point and the last assessment time point (Week 52 LOCF) as well as changes from baseline will be determined.

Rationale for target number of subjects

To verify the safety of long-term administration, the target number of subjects to complete 52 weeks of administration was set at around 100 subjects. Due to the availability of data on safety in elderly subjects from foreign clinical trials, the sample size needed to assess the safety of brexpiprazole in the elderly was set as 30 new subjects (elderly subjects of age 65 and above) receiving IMP administration.

Trial Duration: 01 Jun 2018 to 31 Jul 2022

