### 3.4.2 Inclusion Criteria

Subjects must meet the inclusion criteria described in Table 3.4.2-1. For both rollover subjects from the double-blind trial (331-102-00058) and new subjects, those meeting all the inclusion criteria below at screening (for new subjects only) and baseline are eligible for selection.

Table 3.4.2-1 Inclusion Criteria	
Rollover Subjects	
1	Outpatients
2	Subjects completing the double-blind period (Phase B) of the double-blind trial (331-102-00058) who are able to commence treatment within 28 days from Week 6 of the double-blind period (Phase B) of the double-blind trial (331-102-00058)
3	Subjects who have a level of comprehension sufficient to allow them to give written informed consent to all of the observation/examination/evaluation items specified in the protocol, and who can understand the contents of the trial
4	Subjects with a DSM-5 classification-based diagnosis of "major depressive disorder, single episode" or "major depressive disorder, recurrent episode"
New Subjects	
5	Outpatients
6	Male and female patients $\geq$ 65 years of age (at the time of informed consent)
7	Subjects who have a level of comprehension sufficient to allow them to give written informed consent to all of the observation/examination/evaluation items specified in the protocol, and who can understand the contents of the trial
8	Patients with a DSM-5 classification-based diagnosis of "major depressive disorder, single episode" or "major depressive disorder, recurrent episode" whose current episode has persisted for at least 8 weeks

Table 3.4.2-1 Inclusion Criteria	

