C-SSRS	•	• f	•	•	•	•	•	•	•	•	•	•	•	•	•	•	•	•	•	•	•	•	•	•
DIEPSS		• f	•	•	•	•	•	•	•	•	•	•	•	•	•	•	•	•	•	•	•	•	•	•
AIMS		• f	•				•				•									•	•			
BARS		• f	•				•				•									•	•			
Blood sampling for DNA storage						• i														• i				

Table 3.7-1		Schedule of Assessments																		
Test Period (Acceptable Window)	Items	Treatment Period															Post-treatment observation periodj 30 days after final dose (± 5 days)			
		At screening (new subjects)b	At baseline (rollover subjects)	At baseline (new subjects)	Week 1 (± 2 days)	Week 2 (± 2 days)	Week 4 (± 2 days)	Week 8 (± 7 days)	Week 12 (± 7 days)	Week 16 (± 7 days)	Week 20 (± 7 days)	Week 24 (± 7 days)	Week 28 (± 7 days)	Week 32 (± 7 days)	Week 36 (± 7 days)	Week 40 (± 7 days)		Week 44 (± 7 days)	Week 48 (± 7 days)	Week 52 (± 7 days)
Adverse events		←-----→																		
IMP and requisite concomitant medicationa				•	•	•	•	•	•	•	•	•	•	•	•	•	•	•	•	
Concomitant drugs/therapies		←-----→																		

a Treatment compliance regarding IMP and requisite concomitant medication will be recorded.

b Clinical laboratory test values and body weight values at screening will be used as baseline values.

c For this item, subjects will be asked to visit the trial site in a fasting state (a fast for at least 8 hours [including drinks containing sugar, such as juice]) at screening, baseline, and Week 52, and in a fasting state to the extent possible at other times, including at the discontinuation examination.

d Informed consent will be obtained after the observations, examinations, and assessments at Week 6 of the double-blind period (Phase B) of the double-blind trial (331-102-00058) and before the baseline assessments for this trial.

e Data taken at screening for the double-blind trial (331-102-00058) will be used as the subject demographic data for rollover subjects (date of birth, sex, childbearing potential, race, ethnicity, country where trial is performed, history of major depressive disorder, medical history, complications). Medical history and complications will be reinvestigated.

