#### **3.7.1.2 Screening (New Subjects Only)**

After acquisition of informed consent and within 28 days before commencement of the treatment period, the investigator or subinvestigator will perform the examinations and assessments at the screening (Table 3.7-1) and record the results in the source documents and CRF, and will also judge subject eligibility for trial participation. The investigator or subinvestigator will then record enrollment status, date of enrollment, and reasons for any failed enrollment in the subject screening log.

The investigator or subinvestigator will examine the following subject demographics and record the results in the source documents and the CRF. Regarding the treatment history for the current major depressive episode, all antidepressant prior medications and their effectiveness, as well as psychotherapies/somatic therapies up until 6 weeks before informed consent will be examined. To determine their effectiveness, the results of evaluation will be classified as < 25% Improvement, 25% to 49% Improvement, 50% to < 75% Improvement, and  $\geq$  75% Improvement (complete recovery from depressive symptoms and not the slightest improvement considered as 100% and 0%, respectively), based on the patient's self-evaluations.

- Date of visit
- Subject demographics
  - Date of investigation
  - Date of birth

- Sex
  - Race
  - Ethnicity
  - Country where trial is performed
  - DSM-5-based diagnostic name and severity as well as specific terms (with anxious distress, with mixed features, with melancholic features, with atypical features, with mood-congruent psychotic features, with mood-incongruent psychotic features, with catatonia, with peripartum onset, and with seasonal pattern)
  - Date of first onset of major depressive disorder
  - Frequency of major depressive episodes
  - Date of onset of the current depressive episode
  - Prior medication used to treat the current major depressive episode (all antidepressants)
  - Prior therapy used to treat the current major depressive episode (psychotherapies/somatic therapies up until 6 weeks before informed consent)
  - Frequency of appropriate antidepressant drug treatments of the current major depressive episode (treatment for at least 6 weeks at the approved dose for the antidepressant, or treatment for at least 3 weeks with combination therapy)
  - All prior medications and therapies used within 30 days before acquisition of informed consent

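### SAP 7.3 sets an unknown onset month to June with no cap, so a same-year onset can give a negative, zero or under-8-week episode duration in the baseline tables

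*SAP*

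**What the plan says.** SAP 7.3 (Baseline Disease Evaluation) reports two durations, that of the current episode and that from initial onset. Both use the formula "duration (months) = (date of subject demographic evaluation – date of onset + 1) / 30". Incomplete dates follow one rule: "Any unknown month or day of onset will be replaced with June or 15, respectively". Neither document says that an imputed date must not fall after the evaluation date, or must agree with the eligibility criteria or with the other onset date.

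For new subjects, Protocol 3.7.1.2 has the site record "Date of onset of the current depressive episode" at screening, without requiring the month to be known. Inclusion criterion 8 (Protocol 3.4.2) admits new subjects "whose current episode has persisted for at least 8 weeks". Rollover criteria 1 to 4 give no minimum episode duration. Rollover data come from the earlier trial: a footnote to Protocol Table 3.7-1 states "Data taken at screening for the double-blind trial (331-102-00058) will be used as the subject demographic data for rollover subjects", and SAP 7.3 states "For the other demographic characteristics, baseline data in the double-blind trial (331-102-00058) will be used".

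SAP 7.2 defines descriptive statistics as mean, standard deviation, minimum, median and maximum. The results go into tables CT-3.2.1.1 to CT-3.2.2.9, which cover two analysis sets, each overall and for eight antidepressants.

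**The concern.** A mid-year default works for an onset in a past year. For an onset in the evaluation year it can fall after the evaluation date, or too close to it. The formula then returns a duration that cannot be true, or one shorter than entry required.

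The minimum is among the reported statistics, so one such record is enough to put a negative duration in a table. The tables by antidepressant split the sample eight ways, so a single value could also move a mean or standard deviation visibly. A duration under 8 weeks in a new subject would look like a breach of criterion 8 when only the imputation caused it.

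**Working it through.** **Inputs.** Formula and imputation rule: SAP 7.3. Minimum current-episode duration for new subjects: 8 weeks = 56 days = 56/30 = 1.87 months (criterion 8). Calendar: "Trial Duration: 01 Jun 2018 to 31 Jul 2022" (Protocol Synopsis). The plan gives no figure of its own to reproduce.

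**Are early-year evaluations possible?** Treatment of 52 weeks (364 days) plus 30 days of follow-up is 394 days. Counting back from 31 July 2022 puts the last start of treatment at about 2 July 2021. New subjects could therefore be screened between January and mid-June in 2019, 2020 and 2021.

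**Month unknown, onset year = evaluation year.** Days = evaluation date − 15 June + 1; months = days/30. For 2019:

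| Evaluation | Days | Months |
|---|---|---|
| 25 Feb | −109 | −3.63 |
| 1 Apr | −75 + 1 = −74 | −2.47 |
| 1 May | −44 | −1.47 |
| 13 Jun | −1 | −0.03 |
| 14 Jun | 0 | 0.00 |
| 15 Jun | 1 | 0.03 |
| 1 Jul | 17 | 0.57 |
| 8 Aug | 55 | 1.83 |
| 9 Aug | 55 + 1 = 56 | 1.87 |
| 1 Nov | 140 | 4.67 |
| 31 Dec | 200 | 6.67 |

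A same-year episode can first reach 56 days on 25 February (1 January + 55 days). From then to 31 December 2019 there are 310 evaluation dates: 109 (35%) give a negative value, 1 gives zero, 55 (18%) give 1 to 55 days and 145 (47%) give at least 56 days. In 2020 the split of 311 dates is 110, 1, 55 and 145.

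These are shares of calendar dates. Weighting each date by the number of eligible same-year onsets it allows, and assuming uniform dates, gives about 12% negative, 16% positive but under 8 weeks and 72% eligible. Even this applies only to records with an unknown month and a same-year onset.

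**Only the day unknown.** The largest forward shift is from the 1st to the 15th, 14 days. An episode of exactly 56 days then shows as 56 − 14 = 42 days (1.40 months). Over all 2019 combinations with a true duration of at least 56 days, 42 was the minimum and no value was negative.

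**First onset.** The same rule can put first onset after current onset. As an illustration, take current onset 10 March 2019, first onset known only as 2019, and evaluation on 1 September 2019. Current duration is (175 + 1)/30 = 5.87 months; duration from first onset is (78 + 1)/30 = 2.63 months.

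**Effect of one record.** Take a new subject evaluated on 1 April 2019. The true duration lies between 56 and 91 days (onset 5 February back to 1 January). The error is between (56 + 74)/30 = 4.33 and (91 + 74)/30 = 5.50 months. Among the 30 planned new subjects, the mean falls by 4.33/30 = 0.14 to 5.50/30 = 0.18 months and the minimum becomes −2.47.

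**The case against.** The strongest reply is that the situation is rare and the variable matters little. Sites must record the onset date and confirm at least 8 weeks. Criterion 9 requires at least one antidepressant treatment of 6 weeks or more in the current episode, and Protocol 3.7.5 has treatment dates recorded. A new subject with a recent onset and no known month is therefore unlikely. Unknown months are more plausible for older onsets, where the rule does no such harm. A data query might also recover the month, in which case the rule never applies. All of this stands, and it is why the correct statement is that the rule can give such values, not that it will.

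Several stronger readings are tempting but not supported:

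- A reader might infer that any onset in the evaluation year gives a wrong value. From 9 August the result is at least 56 days, and negative values require an unknown month.
- A reader might take 35% as a share of subjects. It is a share of calendar dates, and the documents give no count of incomplete onset dates.
- A reader might infer that ineligible subjects were enrolled. The investigator judges eligibility at the site, not from an imputed value.
- A reader might extend the 8-week conflict to rollover subjects. These documents state no minimum for them, and the earlier trial's criteria are not available here.
- A reader might suppose that efficacy or safety results are affected. No endpoint or safety analysis uses this variable, and SAP Section 6 states "Neither primary nor secondary outcome variables are planned".

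What the reply does not remove is that a written rule, applied as stated, returns an impossible value, and nothing elsewhere corrects it.

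**Conclusion.** Wrong as written, minor. The windows for negative, zero and short durations follow directly from the SAP formula and need no assumption beyond an unknown month and a same-year onset. The 12%, 16% and 72% split also assumes uniform dates. The conflict with criterion 8 can be shown for new subjects only. The consequence stays within the 18 descriptive baseline disease tables (two sets of nine), where one affected subject could set a negative minimum. The overall size is unknown because the number of subjects with an unknown onset month is not given.

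**What to change.** Add three limits to SAP 7.3:

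1. No imputed onset date may be later than the demographic evaluation date.
2. For the current episode in new subjects, an imputed onset may not be later than 55 days before that date, which is 56 days under the +1 formula.
3. An imputed first-onset date may not be later than the current-episode onset.

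The first limit alone removes negative and zero values but not durations under 8 weeks. The second should not be applied to rollover subjects without a minimum taken from the earlier trial's own criteria.

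With the limits in place, new-subject evaluations on 1 March, 1 May and 1 July 2019 give 1.87 months instead of −3.50, −1.47 and 0.57; 1 November stays at 4.67.

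The cost is a short SAP addition and a few lines of code, with no new data. The downside is that capped subjects are placed at the shortest duration possible for them, so a table footnote giving the number capped would help.
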